Protocol

Version 2.0

Normal Saline Infusion for Stroke after Intravenous Thrombolysis

A Randomized Clinical Trial

Principle Investigators

[name], [name]

Table of Contents

Study Synopsis	4
Abbreviation	8
1. Background	10
2. Objectives	11
2.1 Hypothesis tested	11
2.2 Primary objective	11
2.3 Secondary objective	11
3. Study Design	11
3.1 Trial plan	11
3.2 Selection criteria	12
3.3 Follow-up time point	14
3.4 Randomization and masking	14
4. Trial Flow Chart	15
5. Interventions	16
6. Measurement	16
6.1 Haematological examination and laboratory assessment	16
6.2 Imaging test	16
6.3 Clinical observation	17
7. Outcomes	17
7.1 Efficacy outcomes	17
7.2 Safety outcomes	18
8. Study flow diagram	18
9. Study periods	19
9.1 Screening periods	19
9.2 Treatment periods	19
9.3 In-hospital periods	19
9.4 Follow-up periods	19
10. Adverse events monitoring	19

10.1 Adverse events (AEs)	19
10.2 Serious adverse events (SAEs).....	19
10.3 Safety assessment.....	20
10.4 Severity categorization and relationship definitions of AEs.....	20
11. Statistics	21
11.1 Sample size.....	21
11.2 Statistical analysis.....	21
11.3 Analysis population	22
12. Data management and monitoring.....	22
12.1 Case Report Forms (CRF).....	22
12.2 Monitoring	23
13. References.....	23
Appendix.....	26

Study Synopsis

Title	Normal Saline Infusion for Stroke after Intravenous Thrombolysis A Randomized Clinical Trial
Principle Centre	Tianjin Medical University General Hospital
Objective	To explore the safety and efficacy of immediate abundant normal saline infusion after intravenous thrombolysis for patients with stroke.
Efficacy Outcomes	
Primary outcome
 
 1. Proportion of the patients with mRS 0-2 at 90 days after randomization. 
Secondary outcomes
 
 1. Proportion of the patients with early neurological deterioration (END, ΔNIHSS\geq2 and ΔNIHSS\geq4) at 24 hours after randomization. 2. Proportion of the patients with cerebrovascular events within 1 days, 7 days and 90 days after randomization. 3. Peripheral blood inflammatory indices and laboratory examination (S100-β, brain derived neurotrophic factor and myeloperoxidase). 4. NIHSS scores at 7 days. 5. mRS scores at 30 days and 90 days. 6. Barthel index scores at 30 days and 90 days.
Safety Outcomes	
 1. Ejection fraction within 72 hours. 2. Mortality within 90 days 3. Proportion of intracranial hemorrhage (ICH) and symptomatic ICH within 7 days. 4. Infarction volume at 24 hours after randomization. 5. Blood pressure fluctuation within 24 hours.
Trial Design	NS-STAR is a prospective, multicentre, randomised, open-label, blinded outcome reading, Phase II trial (PROBE design). Subjects included are randomly assigned into the NS group and the control group. Follow-up is performed at baseline, 24 hours, 7 days, 30 days and 90 days after randomization. The outcome assessors are blinded to the allocation

	assignment.
Trial Population	Patients with acute ischemic stroke treated by intravenous thrombolysis
Sample Size	240
Inclusion Criteria	
 1. Acute ischemic stroke. 2. Age 18-80 years. 3. Pre-stroke mRS≤1. 4. NIHSS score 0-25 5. Onset-to-needle time≤4.5 h. 6. Sign the informed consent.
Exclusion Criteria	
 1. Thrombolysis contraindication. 2. Allergy to alteplase. 3. intention to undergo emergency endovascular treatment. 4. Any terminal illness such that patients would not be expected to survive>1 year. 5. Poor compliance. 6. Participating in other clinical trials within previous 3 months.
Withdrawal Criteria	
 1. Acute heart failure during interventions. 2. Hypertensive crisis during interventions. 3. Edema, such as pulmonary edema, limb edema and water intoxication. 4. Other severe complications that should terminate the interventions immediately. 5. Stroke mimics. 6. Decide to undergo emergency endovascular treatment during interventions. 7. Refuse subsequent treatment and follow-up.
Trial Cycle	All included patients are followed-up at baseline, 24 hours, 7 days, 30 days and 90 days after randomization, respectively.
Treatment Regimens	Eligible patients are randomly (a ratio of 1:1) assigned into the NS group: undergoing immediate 2000 mL intravenous infusion of NS after intravenous thrombolysis at a speed of 200 mL/h, or the control group: receiving

	200-400ml of NS after intravenous thrombolysis. A standard therapy according to Chinese guidelines for diagnosis and treatment of acute ischemic stroke 2023 will be performed during the whole treatment period.
Procedure	
Before intravenous thrombolysis: The investigators will collect demographic characteristics, medical history, blood pressure, brain imaging (either computer tomography or magnetic resonance imaging), neurological measurements (NIHSS score and mRS score), haematological examination (blood routine, creatinine, urea, brain natriuretic peptide, etc.), laboratory examination (S100-β, brain derived neurotrophic factor and myeloperoxidase) and other pertinent information.
 
After intravenous thrombolysis: The informed consent will be obtained and patients will be randomly assigned into the NS group and the control group. The investigators will then collect blood pressure and neurological measurements (NIHSS score).
 
24-48 hours after randomization: Brain imaging (either computer tomography or magnetic resonance imaging) will be performed at 24 hours. The 24-hour NIHSS score will be assessed and cerebrovascular events occurring within 24 hours will be recorded. Blood routine and laboratory examination (S100-β, brain derived neurotrophic factor and myeloperoxidase) will also be collected.
 
72 hours after randomization: Cerebrovascular imaging (either computer tomography angiography or magnetic resonance angiography) and an ultrasonic cardiogram will be conducted within this period.
 
7 days after randomization: Neurological measurements (NIHSS score and mRS score) will be evaluated. Cerebrovascular events during this 7-day period will also be recorded.
 
30 days after randomization: The mRS score and Barthel index score will be assessed and cerebrovascular events or other adverse events will be recorded via a telephone interview.

	90 days after randomization: The mRS score and Barthel index score will be again assessed and cerebrovascular events or other adverse events will be recorded via a telephone interview.
Concomitant Treatment	Guideline based treatment.
Statistical analysis	The primary outcome is performed in the intention-to-treat populations as well as per-protocol populations. Sensitivity analyses are performed as well in order to find out the influence factors. The χ^2 test is used in the unadjusted analysis. Modified Poisson regression model with robust error estimation is used in analysis of the primary outcome and other dichotomous end points, with adjustment for prespecified covariates. The relative risk with their 95% confidence interval is calculated in both unadjusted and adjusted analysis. Generalized linear models are conducted for analyse continuous end points. The full range score on mRS is analyzed by an ordinal logistic-regression model, and odds ratios with 95% confidence interval are calculated. No interim analyses are performed in this study. A 2-sided P value <0.05 is considered statistical significance. Because multiple comparisons potentially cause type I error, findings for secondary outcome analyses should be interpreted as exploratory. SPSS software (version 26, IBM) and R software (version 4.1.0) are used for the statistical analyses.
Sites Number	3 centers
Collaborators	Affiliated Hospital of Jiujiang University Cangzhou Hospital of Integrated Traditional Chinese and Western Medicine
Duration	Enrollment about 1 year

Abbreviation

END, early neurological deterioration

NIHSS, National Institutes of Health Stroke Scale

mRS, Modified Ranking Scale

BI, Barthel Index

ICH, intracranial hemorrhage

IVT, intravenous thrombolysis

AIS, acute ischemic stroke

CBF, cerebral blood flow

NS, normal saline

ESO, European Stroke Organisation

CT, computed tomography

MRI, magnetic resonance imaging

BNP, brain natriuretic peptide

MBP, myelin basic protein

GFAP, glial fibrillary acidic protein

MRA, magnetic resonance angiography

CTA, CT angiography

SBP, systolic blood pressure

DBP, diastolic blood pressure

NLR, neutrophil-to-lymphocyte ratio

PLR, platelet-to-lymphocyte

LMR, lymphocyte-to-monocyte

AEs, adverse events

SAEs, serious adverse events

RR, relative risk

GLMs, Generalized linear models

OR, odds ratio

ITT, Intention-To-Treat

PP, Per protocol

CRF, Case Report Forms

1. Background

It is well acknowledged that intravenous thrombolysis (IVT) is a safe and effective strategy for treating acute ischemic stroke (AIS) within 4.5 h in clinical settings.[1, 2] However, only approximately 30% of patients achieve long-term independence (modified Ranking scales 0-1).[3] A plethora of factors may influence the effectiveness of IVT, including age, comorbid diseases, stroke subtypes, infarct size and onset-to-needle time.[3, 4] Ultimately, all these factors can be attributed to reperfusion and the penumbra.[5] Therefore, the further elevation of the reperfusion rate and expansion of the ischemic penumbra after IVT are emerging challenges. A simple approach is to increase cerebral blood flow (CBF), which can reopen occluded vessels and rescue ischemic neurons after AIS. Intravenous administration of 0.9% normal saline (NS) is an easy-to-use strategy commonly used to expand volume.[6, 7] The benefit of NS infusion on stroke outcomes is not a concern, but for reperfusion therapies such as IVT, it seems to be practicable.

Investigations on volume expanders and hemodilution date back to the 1960s.[8] Since then, accumulating evidence has indicated that volume expansion can improve the collateral circulation status, reduce blood viscosity, and alleviate brain dysfunction.[9-12] Considering rescuing the ischemic penumbra, the early use of hemodilution, especially within 6 h after AIS onset, is inevitable to exert its powerful functions.[13] The no-reflow phenomenon and unexpected re-occlusion may be responsible for poor outcomes and early neurological deterioration (END) after IVT.[14] In theory, the early use of hemodilution after IVT can increase distal arterial perfusion and reduce the re-occlusion rate by increasing CBF. In addition, the prevalence of dehydration accounts for approximately 48%-53% of patients with stroke, in whom immediate fluid intake might improve their short- and long-term prognoses, especially in people undergoing thrombolysis.[15-19] Therefore, we hypothesized that immediate hemodilution after IVT may increase the reperfusion rate, reduce the re-occlusion rate, and improve prognosis.

To verify our hypothesis, we administered an intravenous NS infusion immediately after IVT termination. Generally, hemodilution-related drugs include colloids (such as hydroxyethyl and dextrose) and crystalloid (such as NS). An appropriate solution for hemodilution should be provided to optimize the perfusion of vital organs and avoid fluid overload. Although colloids can increase left ventricular end-diastolic volume, stroke volume, and cardiac output, they are also associated with high blood pressure, susceptibility to allergy, heart failure, and higher morbidity and mortality.[7] Compared

to colloids, crystalloids have an equivalent effect on stroke volume variability, which reflects fluid responsiveness.[7] Therefore, these two solutions are considered to have similar effects on fluid resuscitation, and crystalloids seem safer for patients with stroke undergoing reperfusion therapy. Therefore, NS may be a promising therapeutic strategy for volume expansion following IVT.

2. Objectives

This novel study explores the safety and efficacy of NS infusion for patients with stroke after IVT. This trial provides an innovative strategy for facilitating functional independence after the administration of IVT in patients with stroke.

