3.4 Randomization and masking

All patients are enrolled consecutively and randomized in 1:1 ratio to receive NS 2000ml or 200-400ml using a computer-generated randomization code. Sealed envelopes containing the allocation information (NS or control) will be labeled with sequential numbers prepared by an investigator who does not know screening of subjects. The researchers will enroll potential patients with a sequential number of opaque sealed envelopes, which will be opened only after obtaining informed consent. It is ensured that investigators are masked to the treatment allocation.

This is an open label trial, so we adopt a partial blinding strategy where the clinical assessors are blinded but the operators are not. That is, the neurological functional scores, imaging tests and laboratory assessments are assessed by investigators blinded to the intervention and grouping. The operators responsible for NS infusion to the patients are unblinded.

4. Trial Flow Chart

STUDY PROTOCOL									
	Enrollment	IVT ending	Interventions	Follow-up					
TIMEPOINTS	-1 h	0 h	0-10 h	24 h	48 h	Day 3	Day 7	Day 30	Day 90
ENROLLMENT									
Eligible Screen	X								
Informed Consent		X							
Allocation			X						
Termination Screen				X					
INTERVENTIONS									
NS 2000 mL				→					
NS 200-400 mL				→					
ASSESSMENT									
Baseline Data	X								
NIHSS score	X	X		X		X			
Cranial CT	X				X				
Blood Indices	X				—				
Laboratory examination	X				—				
Ultrasonic Cardiogram					—				
Cranial MRA/CTA					—				
Blood pressure					—				
mRS						X	X	X	

IVT: intravenous thrombolysis; NS: 0.9% normal saline; NIHSS: Institute of Health Stroke Scale; CT: computed tomography; MRA: magnetic resonance angiography; CTA: computed tomography angiography; mRS: modified Ranking scales.

5. Interventions

All patients within 4.5 hours from the definite onset time will be screened by the criteria of IVT recommended by European Stroke Organisation (ESO) guidelines.[20]

During thrombolysis, the patient or his certigiers will decide whether to participate in this trial. If they agree, an informed consent for NS-STAR trial will be signed, and allocation will proceed.

Participants will be allocated into two arms:

the NS group, undergoing immediate 2000 mL intravenous infusion of NS after IVT at a speed of 200 mL/h.

the control group, receiving 200-400ml of NS after IVT.

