6.1 Haematological examination and laboratory assessment

Baseline blood samples are obtained before IVT administration. The blood indices comprise blood routine, creatinine, urea, BNP, electrolyte and coagulation function. The blood routine is reassessed at 24-48 hours after randomization. Peripheral blood biomarkers that can reflect brain injury, including S100- β , brain derived neurotrophic factor (BDNF) and myeloperoxidase (MPO) are assessed before IVT administration and at 24-48 hours after randomization.

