9.1 Screening periods

Before IVT administration, enrollment screening and collection of demographic features, medical history, onset-to-needle time, cranial CT imaging, blood pressure, neurological measurements (NIHSS score and mRS score), haematological examinations (blood routine, creatine, urea, BNP, electrolyte, coagulation function and laboratory biomarkers including S100- β , BDNF and MPO), and other information are necessary.

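### The S100-β, BDNF and MPO baseline is collected before consent is sought, with no stated basis, and the analysis plan then never uses it.

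*Combined protocol and SAP*

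**What the plan says.** **Sampling.** The synopsis (Procedure) lists, under its step before thrombolysis, "laboratory examination (S100-β, brain derived neurotrophic factor and myeloperoxidase) and other pertinent information". Section 6.1 says "Baseline blood samples are obtained before IVT administration" and, of the three biomarkers, that S100-β, BDNF and "myeloperoxidase (MPO) are assessed before IVT administration and at 24-48 hours after randomization". Section 9.1 counts "coagulation function and laboratory biomarkers including" the same three among the items it calls necessary before IVT. The Section 4 flow chart, as far as the broken table can be read, marks the laboratory examination in the -1 h column.

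**Consent.** Under its step after thrombolysis, the synopsis says: "The informed consent will be obtained and patients will be randomly assigned into the NS group and the control group". Section 5 says "During thrombolysis, the patient or his certigiers will decide whether to participate in this trial", followed by "If they agree, an informed consent for NS-STAR trial will be signed, and allocation will proceed". The flow chart appears to put consent at the end of IVT.

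**Use of the markers.** They are secondary outcome 9 in Section 7.1.2, defined as values at 24-48 hours. They appear in none of the criteria in Sections 3.2.1 and 3.2.2. Section 11.2 names four adjustment covariates (age, sex, NIHSS after IVT, and time from onset to needle) and no baseline biomarker.

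**The concern.** Two separate things look wrong.

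The first is the order of events. Section 6.1 lists the three markers apart from the clinical blood indices, and they play no part in selecting patients. Their only stated purpose is research, yet their baseline collection comes before the patient or representative is asked. The group affected is wider than the randomised patients. It includes those who decline, and those excluded for haemorrhage during IVT or for having thrombolysis stopped (Section 3.2.2, items 4 and 6), which can be known only after the pre-IVT sample. Three centres would have to decide for themselves on what basis to collect or keep this material.

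The second is that the plan collects a baseline and gives it no role in the analysis. A pre-randomisation measurement of the same marker is the natural covariate for the follow-up value, and omitting it gives up precision in a trial of only 240 patients.

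**Working it through.** **Step 1: order of events.** No arithmetic applies, so the passages are set side by side.

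| Source | Biomarker baseline | Consent |
|---|---|---|
| Synopsis, Procedure | before IVT | after IVT |
| Section 4 flow chart (as legible) | -1 h | 0 h, end of IVT |
| Section 5 | not stated | decision during IVT, then signature, then allocation |
| Section 6.1 | before IVT | not stated |
| Section 9.1 | before IVT | not stated |

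Whichever consent time is taken, the sample precedes it. The consent times themselves also differ (during IVT against after IVT). Section 3.4 ensures that consent precedes opening of the envelope, which protects allocation but says nothing about earlier sampling.

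**Step 2: is a basis for the early collection given?** The supplied text describes no deferred consent, no waiver, no use of leftover clinical blood, and no rule for samples from people who do not join. Section 3.1 reports ethics approval without mentioning this step.

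**Step 3: is the baseline used?** Outcome 9 is the 24-48 h value, not a change from baseline. The covariates in Section 11.2 are attached to the modified Poisson model for dichotomous endpoints. The sentence on generalized linear models for continuous endpoints names no covariates, and its list of examples does not include the biomarkers. The baseline biomarkers therefore enter no specified analysis.

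**Step 4: what would using it gain?** Let r be the correlation between the baseline and the 24-48 h value of the same marker, on the scale analysed. The documents give no value, so 0.3 to 0.6 is an assumption. Adjusting for the baseline multiplies the residual variance by 1 - r², so the sample-size-equivalent factor is 1/(1 - r²), and the standard error is multiplied by √(1 - r²).

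| r (assumed) | 1/(1 - r²) | 240 adjusted patients are worth, unadjusted | Standard error multiplier |
|---|---|---|---|
| 0.3 | 1/0.91 = 1.10 | 240/0.91 = 264 | √0.91 = 0.95 |
| 0.5 | 1/0.75 = 1.33 | 240/0.75 = 320 | √0.75 = 0.87 |
| 0.6 | 1/0.64 = 1.56 | 240/0.64 = 375 | √0.64 = 0.80 |

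These figures assume a baseline for all 240 patients. Missing baselines reduce the gain.

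**The case against.** The strongest reply is that nothing improper has been shown. Section 6.1 already requires routine blood before IVT and nowhere orders a separate tube or draw for the biomarkers. Leftover routine blood assayed after consent would respect both the sampling time and the consent step. The consent pages are missing from the supplied text and could cover earlier samples. Section 12.1 requires a case report form only for randomised participants, so nothing shows that study data are kept on people who decline. All of this stands. It limits the conclusion to an unstated basis and does not establish a breach. It does not remove the need to state the basis, because the procedural sections describe collection before consent and mention none of these routes.

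Three stronger readings are tempting, and the documents do not support them.

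- A reader might infer that sites must either take research blood without consent or lose the baseline. The leftover-blood route shows that this is not forced.
- A reader might infer that a missing baseline would wreck the analysis of outcome 9, because Section 11.2 fills missing baseline variables only below 10%. That rule covers variables in the covariate-adjusted analyses, and no baseline biomarker is among them. As the plan stands, losing these values would cost the specified analysis nothing.
- A reader might infer that a pre-IVT value is an invalid baseline because thrombolysis lies between it and the saline. It is measured before randomisation in both arms, so it is a valid covariate. The use of the post-IVT NIHSS for early neurological deterioration is that outcome's own definition and sets no rule for biomarkers.

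**Conclusion.** The point holds as a gap in the protocol's account of consent and as an unused baseline. In every version of the timeline the outcome-only biomarkers are collected before the patient is asked, the supplied text gives no basis for it, and the analysis plan does nothing with the result. That they are outcome-only is an inference from their separate listing and their absence from the eligibility criteria; the documents do not use the term.

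The number of people sampled who never join is unknown. The documents give no ratio of screened to randomised patients, and I do not put a figure on it.

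The precision available from using the baseline is a factor of about 1.10 to 1.56, resting entirely on the assumed r. The primary outcome is unaffected, and Section 11.2 already labels secondary findings exploratory. This is a minor-to-moderate point that is cheap to settle. It does not require the sampling time to move to the end of IVT. That would add an uncosted blood draw just after thrombolysis, when saline is due to start at once, and would give up the intended pre-IVT value.

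**What to change.** **(a) Consent and sampling.** Reconcile the synopsis (Procedure), the Section 4 flow chart and Sections 5, 6.1 and 9.1 on when consent is obtained. State that baseline S100-β, BDNF and MPO are assayed only from blood left over from the routine pre-IVT sample, and only once consent is signed. State that leftover blood from people who decline or are not randomised is not assayed. Check that the consent form, not available here, says the same.

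**(b) Analysis.** In Section 11.2, specify that each 24-48 h biomarker value is analysed with the patient's own baseline value of that marker as a covariate. The panel must match for this to work: Section 9.2 lists S100-β, MBP and GFAP at 24-48 h, whereas Sections 6.1 and 7.1.2 list S100-β, BDNF and MPO. These should be aligned in the same amendment.

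**Cost.** Protocol wording, holding leftover routine blood unassayed until consent is known, and one added model term. No extra draw is needed. The downside is that leftover volume may be too small for some patients, so some baselines will be missing. Once the baseline biomarker is a covariate, the Section 11.2 filling rule would apply to it, and that rule stops at 10%, which is 24 of 240 patients. The plan should say what is done at or above that level.
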